sessions so that degree of analgesia achieved from beverage consumption can be assessed relative to a personalized baseline. These calibration trials will consist of an ascending series of thermal pulses starting at 43°C and increasing by 1°C until the participant's tolerance is reached. After each pulse, participants will rate pain intensity using a visual analog scale (VAS). The lowest temperature with a VAS score of 5 will be used for thermal stimuli during laboratory sessions. Next, during both screening and laboratory sessions, we will employ a slowly ramping thermal stimulus (.5°C per second starting at 32°C) delivered to the glabrous skin of the foot. Pain ratings (using a 10 cm VAS ranging from "no pain" to "most intense pain imaginable") will be collected every 5 seconds during this process until the participant's tolerance is reached in order to determine temperatures associated with pain threshold (i.e., temperature at which the stimulus first becomes painful) and tolerance (i.e., temperature at which the stimulus becomes unbearable). This protocol also allows for the examination of pain after-sensation following removal of the thermal probe, a construct related to the clinical experience of chronic pain (Staud et al., 2007). To this end, participants will report current pain levels at 15 and 30 seconds following stimulus removal. VASs are considered the "gold standard" for laboratory and clinical pain assessment given that they have a ratio scale (Price et al., 1983) and are able to effectively separate the sensory (i.e., intensity) and affective (i.e., unpleasantness) components of the pain experience. The investigative team has extensive experience with these procedures, and is confident they can be completed safely and effectively. All thermal stimuli will be delivered using a computer-controlled Q-Sense fMRI Compatible thermal stimulator (Ramat Yishai, Israel), a Peltier-element based device. We propose to utilize a thermal stimulus paradigm because the processing of such stimuli is particularly well understood. Such paradigms have been demonstrated in the broader pain literature to be sensitive to group differences (e.g., chronic pain patients vs. healthy controls), as well as experimental manipulations like acute opioid analgesic treatment and placebo induction (e.g., Chung et al., 2007; Sevel et al., 2015; Staud et al., 2012). Furthermore, its use in this study will enhance comparability to previous work. Following each QST measure during laboratory sessions, participants will be provided with a 10 cm VAS assessing perceived relief from pain resulting from beverage consumption (anchored from "No relief at all" to "Most profound relief imaginable"). QST procedures will require approximately 10 minutes. During laboratory sessions, QST procedures will be administered prior to alcohol consumption to function as a point of reference for participants and again approximately 15 minutes after beverage consumption to allow for absorption of alcohol ([name] et al., 2014).

Neuroimaging Protocol. Neuroimaging data will be acquired using a research-dedicated, whole-body scanner within the McKnight Brain Institute. Using a standard 32-channel RF head coil, we will collect both structural and functional neuroimaging data. A high-resolution, 3D structural scan will first be conducted using a T1- weighted MP-RAGE protocol. This T1-weighted structural image will predominately be used in pre-processing all functional data. Although not a primary aim, assuming sufficient time in a scanning session, we will also collect magnetic resonance spectroscopy (MRS) data using a brief sequence (~3-4 minutes) so that brain neurotransmitter and ethanol levels can be measured in regions relevant to pain processing and alcohol intoxication.

Following these structural scans, functional imaging data acquisition will occur using two paradigms described below: 1) resting-state scanning, and 2) noxious thermal stimulation protocol. In total, participants will complete two resting-state scans and three task-based fMRI runs, amounting to a one-hour scanning session. Of particular importance is minimizing head motion during scanning when participants are intoxicated, as head motion has been shown to affect data quality (Goto et al., 2015). We will ensure that participants' heads are heavily padded inside the head coil prior to scanning, and will use the Artifact Detection Tool to remove confounds of motion during pre-processing of data. Participants will be reminded of the importance of staying awake throughout the scanning process, and we will check in with participants between each scan to ensure they did not fall asleep. [name] will work with [name] to continually monitor data quality throughout the project.

Resting-State Scanning. First, participants will complete two resting-state (i.e., task-free) scans while keeping their eyes open and focused on a fixation cross. Resting-state fMRI is a powerful tool used to elucidate large- scale neural networks underlying human brain architecture (Biswal et al., 2010). Of these intrinsic connectivity networks, the subcortical limbic network is most relevant to the current project. Although previous studies have examined this resting-state network in the context of heroin (Schmidt et al., 2015) and tobacco (Janes et al., 2012) dependence, intrinsic connectivity of this network has yet to be explored in the context of acute alcohol effects. This project will use a resting-state fMRI protocol to examine differences in subcortical limbic system connectivity (as well as other pain- and reward-related resting state networks) between groups at baseline, as well as between conditions to determine whether acute alcohol consumption differentially disrupts this network in individuals with a family history of alcoholism. One resting state scan will use a conventional BOLD-sensitive T2* weighted sequence. The other will use a partial-continuous arterial spin labeling (pCASL) sequence because these scans yield estimates of cerebral blood flow (CBF) which can be used as covariates in BOLD analysis of subsequent task-based scans, accounting for the cerebrovascular effects of alcohol administration (Marinkovic et al., 2013). Each resting state scan will require approximately 9 minutes.

fMRI Heat Pain Protocol. Three task-based fMRI runs will be conducted subsequent to resting-state scanning using a noxious thermal stimulation protocol. This protocol has been previously used in an NIH-funded study in which [name] is a co-investigator (R01AT006334). For this task, a long MR-compatible thermal probe attached to a Medoc Q-Sense fMRI compatible thermal stimulator will be used to deliver noxious thermal stimuli. Blocks of thermal stimuli will be delivered to the glabrous skin of the foot at the individually calibrated temperature determined during the screening visit. Following each thermal stimulation block, participants will rate levels of pain intensity and perceived relief from alcohol. Each block will be preceded and/or followed by a 30-second rest blocks. An electronic VAS will be presented following each thermal stimulation block for the purposes of rating pain intensity (anchored from "No pain at all" to "Most intense pain imaginable"). After each run, participants will rate their perceived degree of relief from pain as a result of consuming their beverage using an electronic

VAS anchored from “No relief at all” to “Most profound relief imaginable”. Runs will last for approximately 6 minutes, and will take place consecutively.

Power Analysis. Power analysis and recruitment goals are based on results of our pilot study (see attached grant document for a detailed description of results). Power analyses were performed assuming two-tailed hypothesis tests. Effect sizes are reported as Cohen’s d, r, or f^2 (Cohen, 1988).

Our pilot data suggested statistically large increases in pain threshold temperature ($d = 1.16$) associated with BrACs $\sim .052$ g/dL. Effects on pain tolerance temperature and intensity ratings were smaller ($d = .28$); however, our targeted sample of 110 completers will provide $\sim 80\%$ power these effects, and $> 99\%$ power to detect effects of alcohol on pain threshold.

FH of alcoholism was associated with greater expectancy of pain relief from alcohol intake in our pilot work ($d = 1.12$), as well as lower ratings of pain relief ($d = .54$). Effects of sex on these measures were large ($d > .88$). Sex also appeared to be a potent moderator of alcohol analgesia ($d > .90$), with women showing stronger analgesic effects. Our sample will provide $> 80\%$ power to detect these effects. FH was associated with smaller effects on alcohol-related reductions in pain intensity ($d = .42$), as well as pain threshold and tolerance ($d < .26$), resulting in $\sim 54\%$ power to detect interactive effects of FH and dose on these measures.

Across participants, preliminary data suggested small-to-moderate correlations between expectancy of pain relief from alcohol, ratings of pain relief, and typical daily drinking and reductions in pain sensitivity ($.26 < r < .44$). We anticipate $\sim 80\text{-}99\%$ power to detect these effects. However, our data also suggested that sex and FH may moderate these relationships. The interaction of sex and expectancy of pain relief strongly predicted increases in pain threshold and tolerance associated with alcohol intake ($f^2 > 1.11$). A similar effect was detected for the interaction of FH and expectancy of pain relief ($f^2 > .81$). A weaker interaction of FH and ratings of relief on QST measures was also detected ($f^2 > .37$). Likewise, interactions of sex with typical daily drinking and ratings of relief showed some relation to QST changes ($f^2 < .21$). We anticipate $> 94\%$ power to detect each of these interactions. There was little evidence of Sex or FH interactions with typical drinking on alcohol analgesia ($f^2 < .04$). Effect sizes of FH X Sex X expectancy/relief/typical drinking interactions could not be assessed given our limited sample; however, we anticipate sensitivity to detect an interactive $f^2 > .14$ with 80% power given our recruitment target.

Data Analysis Strategy. Data will be analyzed using SPSS 24 (IBM Corp., Armonk, NY).

Aim 1. Test competing hypotheses regarding the effects of family history of alcoholism on alcohol analgesia. To assess hypotheses related to Aim 1, FH status will be included as an independent variable in repeated measures general linear models analyses (rmGLM; SPSS GLM procedure; repeated: dose), with pain threshold/tolerance and intensity ratings, associated relief ratings, expectancy of pain

relief from alcohol, and SEAS measures (i.e., HIGH+, HIGH-, LOW+, and LOW-; Morean et al., 2013, 2015) as dependent variables. Demographic, personality/affective (i.e., BDI/STAI/IRQ/NEO-derived neuroticism), and biomedical (i.e., menstrual phase for female participants, sleep quality) variables will be included as covariates should any be found to correlate significantly with magnitude of alcohol analgesia or relief ratings. A main effect of FH status such that FH+ individuals have greater magnitude of alcohol analgesia (i.e., greater increases in pain threshold/tolerance and decreases in pain intensity ratings), more positive/fewer negative subjective alcohol effects, and stronger expectancy of pain relief from alcohol consumption will be interpreted as evidence in support of H1 and H3. Lower ratings of alcohol-related relief from pain in FH+ individuals will provide support for H2.

To determine the independent contributions of expectancies and typical drinking behavior to alcohol analgesia, these measures will be included as independent variables in separate multiple regression analyses including interaction vectors with sex and FH, with magnitude of alcohol analgesia (e.g., increased pain threshold or reduction in pain intensity ratings) as the dependent variable. They will then be entered into simultaneous regression analysis to assess independence of their effects. A positive association between typical drinking and analgesic response to alcohol will provide support for H4. Risk of Type I error will be mitigated through the use of Tukey's HSD. Although not a primary aim, the relationship between individuals' rate of rise of BAC following alcohol consumption and magnitude of alcohol analgesia will be examined in exploratory analyses. For FH+ participants, potential effects of the sex of affected parents and concordance with the participants' sex (i.e., sex-matched vs. unmatched pairs) will also be assessed.

Aim 2. Imaging functional correlates of alcohol analgesia and its modulating factors.

H5, that alcohol administration will be associated with disruption of BOLD activation in/between regions associated with affective and cognitive aspects of pain processing during application of heat pain stimuli, and H6, that this disruption will be stronger among FH+ individuals, especially within motivation-related structures/circuits, will be evaluated using a two-part process. For all analyses described, motion will be controlled for at the individual subject level (i.e., first level) by including all six movement parameters (x/y/z translation, pitch/roll/yaw) and outlier volumes (determined using the Artifact Reduction Toolbox) as nuisance covariates. We will also co-vary for mean cerebral blood flow measured using pCASL-based resting state scans. Familywise error will be controlled for all analyses using false discovery rate correction (FDR; Benjamini and Hochberg, 1995) at $p < .05$.

Resting-state analyses: Pre-processed resting-state data will be analyzed using hybrid ICA-seed-based fcMRI analyses (Kelly et al., 2010). For this approach, independent components analysis (ICA) and seed- based correlations are used in tandem. First, ICA will be used to empirically derive a priori regions of interest (ROIs) based on resting-state networks identified from the study's participants. Networks of particular interest in this study include those associated with processing of nociceptive stimuli and those that

are disrupted in chronic pain, including default mode network (DMN), salience network (SN), executive control network (ECN), and subcortical limbic network (LN) (Martucci and Mackey, 2016). ICA will be conducted using the voxel-to- voxel processing stream in the CONN toolbox, which involves back-projection of ICs identified across subject and condition to identify spatial components, followed by back-projection of these components to individual subjects (Calhoun et al., 2001). ICs most closely matching networks of interest will be identified based on masks derived from NeuroSynth (Yarkoni et al., 2011). Second, seed-based fcMRI analyses will examine Fishers' r-to-z transformed correlations between the ICA-derived seed ROIs and all other voxels in the brain. Seed-based correlation analyses will be conducted in the Conn Toolbox (Whitfield-Gabrieli & Nieto-Castanon, 2012). Hybrid ICA-seed-based fcMRI has been shown to yield accurate and reproducible results (Franco et al., 2013; Kelly et al., 2010). We will examine interactions of group and condition on connectivity of these resting-state networks using repeated measures GLM, followed by simple main effects decomposition.

Task-based analyses: Alcohol-related changes in BOLD activity in pain- and reward-related brain structures during painful stimulation will be evaluated using a GLM-based approach in SPM12. Following convolution of the canonical hemodynamic response function with the heat stimulation paradigm at the single subject level, group-level effects of dose, sex, and FH on pain-related activations in ROIs and in whole brain will be assessed. To examine the changes in functional connectivity associated with alcohol analgesia, task-based data will be analyzed using the psychophysiological interaction (PPI) pipeline within the Conn Toolbox. PPI is a method of examining task-modulated increases in functional connectivity through GLM by yielding an interaction term (i.e., PPI regressor) from the product of a task's convolved time course (e.g., blocks of noxious thermal stimulation) and the time course from a seed ROI (O'Reilly et al., 2012). Relevant seed ROIs for this analysis will be generated using ICA as described above. We will examine task-dependent functional connectivity in pain- and reward-related networks, both between groups and within conditions, using rmGLM.

Aim 3. Test sex as a moderator of alcohol and FH effects.

To evaluate Aim 3, sex will be included as a factor of interest in rmGLM analyses described under Aims 1 and 2. A sex by dose interaction such that alcohol consumption produces greater reductions in pain sensitivity and higher VAS ratings of relief for women than men will provide support for H7. Presence or absence of a significant sex by family history by dose interactions on metrics of alcohol analgesia will inform Empirical Question 1. Sex will also be included as a factor of interest in analyses of functional neuroimaging data to determine whether sex and FH of alcoholism interact to determine the effects of acute alcohol administration on pain-related brain processes.

7. Possible Discomforts and Risks:

Psychological Discomforts and Risks. Some aspects of the questionnaires utilized in this proposal may make study participants uncomfortable, especially those dealing with affect or medical history. To ameliorate this possibility, participants will be informed they

can withdraw from the study at any time or skip individual questions that may be upsetting to them.

Acute Alcohol Intake. Alcohol intake may result in dizziness, nausea, and vomiting should a participant tolerate the active dose of alcohol poorly. The risk of these as well as more serious consequences may increase if a participant uses medications that contraindicate the use of alcohol (e.g. benzodiazepines/opioid analgesics). Should a participant experience any of these symptoms, they will be allowed to rest until symptoms subside and will be allowed to withdrawal from the study if desired. We have attempted to minimize this risk by recruiting only those who are regular moderate drinkers and excluding those regularly taking prescription medications that contraindicate the use of alcohol. Ss will be rescheduled if they report having taken prescription or over-the-counter medications that contraindicate alcohol use on the day of testing.

Pregnancy: Alcohol intake is an unacceptable risk in pregnancy. Therefore, anyone of childbearing potential will be tested for pregnancy on the morning of the laboratory session. Positive pregnancy tests will result in exclusion from study and lab staff will assist in making a referral as appropriate. Finally, any documents associated with a participant testing positive for pregnancy will be destroyed without reference to a specific cause.

Breath Analyzer Testing: Breath analyzer testing may result in dizziness or lightheadedness for some individuals. However, the PI has administered many of these tests and never observed a significant negative consequence. Staff will be trained to recognize discomfort resulting from breath analyzer testing and will assist participants in ameliorating symptoms should they occur (eg., discontinue testing, place head between knees, etc.).

MRI Scanner. The MRI scanner generates a very powerful magnetic field. To avoid all potential harm to participants as a result of exposure to this field, we will follow all UF CTSI Human Imaging Core screening procedures. By following the Human Imaging Core checklist, we will ensure no participants have metal of any kind implanted in their body, have any pacing devices (i.e., heart pacemaker), metal in their eyes, or certain types of heart valves or brain aneurysm clips. Some participants may also feel anxious about the confined space in the MRI. To attenuate this possibility, participants will be reassured that they can communicate with researchers and MRI staff through a speaker system. They will also be given the option to stop the experiment at any time during scanning. Finally, the MRI system produces very loud noises, which – in very rare cases – can produce hearing loss. To reduce this risk, participants are required to use both earplugs and headphones.

QST Discomfort and Risks. QST, by definition, will induce thermal pain in participants. However, risk of harm as a result of QST procedures is minimal for the following reasons: 1) the pain is transient in nature and generally subsides immediately after the procedure; 2) participants are instructed that they may stop any procedure at any time

with no adverse consequences; 3) the level of pain experienced by participants is below their tolerance level; and 4) although pain sensation may continue after thermode removal (at discretion of the participant), this is not expected to last longer than 90 seconds. Furthermore, because QST instrumentation cannot produce thermal stimuli above 52°C and is equipped with an automatic shutdown system (preventing prolonged delivery of high-intensity stimuli) the risk of burning the skin is very slight. Of over 800 participants tested with QST procedures in the Center for Pain Research and Behavioral Health over several studies, less than 1.5% have suffered a first-degree burn, less than 0.5% have suffered a second-degree burn, and none have suffered a third-degree burn. Should a participant suffer a burn following thermal QST or continued pain 24 hours after pressure pain QST, an adverse event will be reported to the IRB.

Participant Confidentiality Risks. The investigative team places a high priority on protection of patient confidentiality and will use the following procedures to protect patients. Unique participant identifiers will be generated in order to collect protected health information (i.e., from questionnaires) for research purposes. Paper questionnaires and forms will be stored in a locked storage space, digital information will be stored in encrypted, password protected files on secure servers, and the data that links the participants to their unique identifiers will be stored in a separate location. When the study is completed and all raw data is entered electronically, participant identifiers will be destroyed. Despite these efforts, it is possible that participant confidentiality may be breached. If a breach occurs, it will be reported to NIH and the IRB and appropriate measures will be taken. These measures include but are not limited to informing affected participants of the breach and assisting with protective measures once the breach is detected.

Data and Safety Monitoring Plan

Because the proposed study does not comprise a clinical trial, a formal Data and Safety Monitoring Board has not been planned. The investigative team, including Drs. [name], [name], [name], and [name], will meet quarterly to discuss data and safety monitoring issues. Any issues identified during the course of these meetings will be handled in a manner consistent with the University of Florida's policies.

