Aim 1. Test competing hypotheses regarding the effects of family history of alcoholism on alcohol analgesia. A substantial body of evidence suggests that individuals with FH of alcoholism (FH+) have differential subjective responses to acute alcohol administration compared to FH-, including greater pain reduction (Stewart et al., 1995; Ralevski et al., 2010). **Hypothesis (H)1.** We hypothesize that alcohol administration will be associated with greater reduction in pain sensitivity in FH+ than FH- individuals. Based on our pilot data, we also predict **H2.** FH+ individuals will report lower subjective ratings of relief from pain after consuming alcohol. Confirmation would suggest FH+ individuals may self-administer greater quantities of alcohol to achieve pain relief, consistent with the Low Level of Response (LLR) model (Morean and Corbin, 2010). Disconfirmation would suggest the negative reinforcing effects of alcohol

may be especially pronounced in FH+ (i.e., sensitization). Previous studies suggest typical alcohol use, motivations to drink, and personality factors may influence alcohol analgesia, suggesting a critical role of conditioning and expectancies (Brown et al., 1977; Cutter et al., 1979; Ralevski et al., 2010). On the basis of our pilot data, we predict **H3**. FH+ individuals will have stronger positive expectancies regarding alcohol analgesia, which will predict analgesic response to alcohol administration. Results also suggest **H4**. a conditioning effect such that individuals who endorse greater and more frequent alcohol consumption will experience a greater analgesic effect of alcohol.

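### Does Aim 1 let a non-significant difference in relief ratings count as evidence for sensitization, and must the plan add a rule to prevent it?

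*Combined protocol and SAP*

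**What the plan says.** Section 5, Aim 1, predicts in H2 that FH+ participants will rate their relief after alcohol lower than FH- participants. Confirmation is linked to the Low Level of Response model. The next sentence begins "Disconfirmation would suggest the negative reinforcing effects of alcohol" and continues "may be especially pronounced in FH+ (i.e., sensitization", where the bracket closes.

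In section 6, Data Analysis Strategy, Aim 1, the model is a repeated-measures GLM with FH status as a factor and dose as the repeated factor. The relief ratings that go with the pain measures are among the dependent variables. The only criterion for H2 is "Lower ratings of alcohol-related relief from pain in FH+ individuals will provide support for H2". Sensitization is not mentioned anywhere in that section.

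Relief is collected in two settings:
- QST Procedure: "participants will be provided with a 10 cm VAS assessing perceived relief from pain resulting from beverage consumption". QST is done before the drink and about 15 minutes after it.
- fMRI Heat Pain Protocol: one sentence says "Following each thermal stimulation block, participants will rate levels of pain intensity and perceived relief from alcohol". A later one says "After each run, participants will rate their perceived degree of relief from pain as a result of consuming their beverage".

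The Power Analysis states "Power analyses were performed assuming two-tailed hypothesis tests". It reports that FH in the pilot went with stronger expectancy of relief "as well as lower ratings of pain relief" (d = .54), and it claims power above 80%.

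**The concern.** Aim 1 is presented as a test of competing hypotheses, yet H2 has two written outcomes and no third. If a null or imprecise contrast counted as disconfirmation, it would be credited to sensitization, although only higher relief in FH+ supports that theory. A real effect in the H2 direction, but smaller than in the pilot, would then usually be reported as pointing the other way.

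The score is also open. Relief could come from QST or from the scanner, and the scanner text gives both a per-block and a per-run rating. The contrast could be the FH main effect, the FH by dose term, or FH within the alcohol session alone. At stake is a theoretical conclusion that might depend on a definition and a score chosen after the data are seen.

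**Working it through.** **Inputs.** From the plan: 110 completers (Participants); d = .54 for relief and two-tailed tests (Power Analysis). Assumed: a 5% level, which is not stated for the behavioural tests; an FH split of 55:55, with 28:82 as the far end of the range, because no split is stated; and a simple two-group comparison in SD units of the relief score.

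**Reproducing the plan's figure.** The noncentrality is d × √(n1·n2/(n1+n2)) = .54 × √(55·55/110) = .54 × 5.244 = 2.83, on 108 df with critical t = 1.982. Power is .801 (.808 by the normal approximation), which agrees with the stated figure of above 80%. At 28:82 it is .686.

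**Three possible results for the relief contrast** (noncentral t, 108 df):

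| True d (FH+ lower) | Split | Significant for H2 | Not significant | Significant reversal |
|---|---|---|---|---|
| .54 | 55:55 | .801 | .199 | .000001 |
| .54 | 28:82 | .686 | .314 | .000005 |
| .27 | 55:55 | .289 | .711 | .0004 |
| .27 | 28:82 | .230 | .769 | .0007 |
| 0 | 55:55 | .025 | .950 | .025 |

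**Reading A: anything short of confirmation is disconfirmation.** At 55:55 the rate of a sensitization conclusion is 1 − .801 = .199, 1 − .289 = .711 and 1 − .025 = .975.

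**Reading B: disconfirmation means significantly higher relief in FH+.** The rates are the last column: below .0001, .0004 and .025.

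**Reading C: H2 not confirmed and H1 significant.** Take the plan's H1 power of .54 and treat the two tests as independent.
- Pilot relief effect: .54 × .199 = .107.
- FH affects pain intensity but not relief: .54 × .975 = .527.
- FH affects neither: .025 × .975 = .024.

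The power of .54 does not match d = .42 at 55:55, which gives .588. With .588 the first two become .588 × .199 = .117 and .588 × .975 = .573. The middle case is not an error rate: there FH+ participants truly do get more analgesia, and H1 has shown it.

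**Precision.** The 95% CI half-width is 1.982 × √(1/55 + 1/55) = .378 SD (.434 at 28:82). As .378/.54 = .70, an estimate of zero would not exclude a difference of 70% of the pilot effect in either direction. A null result therefore favours neither theory.

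**Choice of score.** With no true difference, the chance that at least one of k independent scores is significant in the H2 direction is 1 − .975^k: .049 for k = 2, .073 for k = 3, .119 for k = 5. Ratings by the same people of the same drinks should be positively correlated, so the real inflation should be smaller.

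**Which reading the text supports.** To disconfirm is to find evidence against, which a non-significant contrast does not supply. The clause "may be especially pronounced in FH+ (i.e., sensitization" names a direction, and a null contrast cannot show an effect that is stronger in FH+. Both verbs in the sentence are tentative, and the sentence gives background to the aim. The section that governs analysis attaches no result to sensitization, so Reading A describes a reporting rule that the plan does not contain.

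**The case for a change.** The strongest reply is that several readings fit and the text does not choose among them. Elsewhere the plan treats a missing effect as informative: under Aim 3, either the presence or the absence of a significant three-way interaction is to answer Empirical Question 1. The plan can also name a contrast when it wants to, since H7, including its relief component, is tied to a sex by dose interaction. H2 has no such link, while H1 and H3 are described through a main effect of FH. The Tukey adjustment selects neither a score nor a contrast.

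Part of this stands. No inconclusive outcome is written for H2, no single relief score or contrast is fixed, and the per-block and per-run sentences on scanner relief do not agree.

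The gap is narrower than it looks, however. The instrument and anchors are given. Relief is asked about the beverage, so a pre-drink rating is not a serious candidate. The relief ratings enter the model alongside the pain measures they accompany, and that model yields both the FH main effect and the FH by dose term. In the scanner text, the more specific later sentences give the block scale to intensity and the run scale to relief, which points to a drafting slip more than to a further outcome. An open choice among scores applies equally to threshold, tolerance and intensity, so it is a general feature of this multi-outcome mechanistic study and not a fault peculiar to H2.

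**Conclusion.** The concern does not call for a change. The large rates (20%, 71% and 97.5% at 55:55) hold only if a null result is treated as disconfirmation, which the plan does not clearly say and its directional wording disfavours. If a significant reversal is required, a wrong sensitization conclusion occurs in at most 2.5% of trials when FH+ relief is truly equal or lower. All these rates rest on 110 completers, a two-sided 5% level and an assumed FH split.

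What is left is an undefined term in the Aims and a score left to the analyst. A competent analyst would use post-beverage relief in the stated model, report the FH estimate with its interval (about ±0.38 SD), and call an interval that includes zero inconclusive. No stated analysis rule has been shown to give a wrong answer, and the plan's power figure for H2 reproduces under an equal split.
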